5.4 Temporal Artery Temperature Measurement and Fever Assessments

Participants' temperatures will be taken using a digital temporal artery thermometer that will be provided to each parent/LAR during enrollment to use for the study and keep for use following the study. The initial temperature will be recorded in the clinic and study staff will demonstrate proper use of the thermometer to the parent. Temperatures will be collected during both Visit 1 and Visit 2. Thereafter, parent(s)/LAR(s) will measure and record the participant's temperature at approximately the same time each day (preferably after 6:00 PM or right before participant goes to bed) beginning on Day 1 (day of vaccination) and will do so through Day 8 following Visits 1 and 2. In addition, parents will be instructed to take a temperature using a temporal artery thermometer if their child feels warm or feverish at any time from Days 1-8 after Visit 1 and 2 and to record the temperature on the memory aid. Temperature measurements will be done for both the simultaneous and sequential groups in a similar fashion such that those children in the simultaneous group, who do not receive vaccinations at Visit 2, will also have temperatures measured. If at any time a temperature $\geq 100.4^{\circ}\text{F}$ ($\geq 38^{\circ}\text{C}$) or $\leq 95^{\circ}\text{F}$ ($\leq 35^{\circ}\text{F}$) is recorded, a second measurement will be taken within 20 minutes. The highest of those two temperature measurements will be recorded. If more than one temperature is taken on the same day (prior to bedtime), the highest temperature for that day should be recorded on either the paper memory aid or entered into REDCap. Any temperature measured after your child's bedtime memory aid entry has been completed, should be considered for the next day's memory aid entry.

All temperatures will be measured using a temporal artery thermometer (Exergen Medical Scanner Model TAT-2000C)^{18,19}. Although parents may elect to use an alternate method for measuring temperatures, they will be required to measure temporal artery temperature measurements as specified above.

For this study, temperatures will be documented using either the electronic memory aid through REDCap or the paper memory aid. The preferred method for documentation in this study is REDCap. All parent(s)/LAR(s) will be encouraged to use the paper memory

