6.2.5 Exploratory Objectives

For exploratory objective 1 the average peak temperature on day 1 and/or 2 following Visit 1, Visit 2 and Visit 1 and 2 combined will be presented by simultaneous and sequential vaccination groups. To evaluate the duration of fever, the number of fever degree-days on day 1 or 2 following Visit 1, Visit 2 and Visit 1 and 2 combined will be presented by simultaneous and sequential vaccination groups. Comparisons will be made using a Mann-Whitney U/Wilcoxon rank-sum test.

For exploratory objective 2 we will present the use of antipyretics for fever on day 1 and/or day 2 after Visit 1 and Visit 2 (separately and combined) in the simultaneous versus sequential group in tables for presentation. The proportion of children with antipyretic use on day 1 and/or day 2 following Visit 1, Visit 2 and Visit 1 and 2 combined will be compared using a Mantel-Haenszel statistic in a stratified analysis by site between the simultaneous and sequential vaccination groups.

Exploratory objective 3 that evaluates the level of severity of fever at various time points, will be presented and compared using a Mantel-Haenszel statistic in a stratified analysis by site.

Exploratory objectives 4 and 5 evaluate fever on days 3-8 and the clinical importance of fever on days 3-8, respectively. We will present and compare the proportions in

objectives 4 and 5 using a Mantel-Haenszel statistic in a stratified analysis by site to control for the randomization blocks. We will adjust for MMR and MMRV receipt at Visit 1 if necessary when analyzing the following outcome measures- EOM5.1, EOM5.2, and EOM 5.3 due to the possibility that a measles-containing vaccine may be administered at Visit 1 to infants in both the simultaneous and sequential group. Also for objective 5, we will present and compare the mean duration of any fever starting on days 3-8 using a Mann-Whitney U/Wilcoxon rank-sum test. Other analysis to further evaluate the clinical importance of fever onset 3-8 days after Visit 1 and/or Visit 2 will be performed if necessary.

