3.3 Exploratory

a)

1. EOM 1.1: Average peak temperature of children with fever (temperature $\geq 38.0^{\circ}\text{C}$ or $\geq 100.4^{\circ}\text{F}$) on day 1 and/or day 2 following Visit 1, Visit 2, and Visit 1 and Visit 2 combined.
2. EOM 1.2: Total number of fever degree-days (temperature $\geq 38.0^{\circ}\text{C}$ or $\geq 100.4^{\circ}\text{F}$) on day 1 and/or day 2 per subject following Visit 1, Visit 2, and Visit 1 and Visit 2 combined.

b) EOM 2.1: Proportion of children with antipyretic use for fever on day 1 and/or day 2 following Visit 1, Visit 2 and Visit 1 and Visit 2 combined.

c)

1. EOM 3.1: Proportions of children with fever at different levels of severity (Grades 1, 2, and 3) on day 1 and/or day 2 following Visit 1 and Visit 2.
2. EOM 3.2: Proportions of children with fever at different levels of severity (Grades 1, 2, and 3) on days 3-8 following Visit 1 and Visit 2.
3. EOM 3.3: The proportion of children with fever at different levels of severity (Grades 1, 2,3 and all Grade) on days 1-8 following Visit 1 and Visit 2.

d)

1. EOM 4.1: Proportion of children with fever (temperature $\geq 38.0^{\circ}\text{C}$ or $\geq 100.4^{\circ}\text{F}$) on at least one day on day 3-8 following Visit 1.
2. EOM 4.2: Proportion of children with fever (temperature $\geq 38.0^{\circ}\text{C}$ or $\geq 100.4^{\circ}\text{F}$) on at least one day on day 3-8 following Visit 2.
3. EOM 4.3: Proportion of children with fever (temperature $\geq 38.0^{\circ}\text{C}$ or $\geq 100.4^{\circ}\text{F}$) on at least one day on day 3-8 following Visit 1 and Visit 2 combined.

e)

1. EOM 5.1: Proportions of children with moderate/severe fever (GRADE 2 and/or 3) on at least one day during days 3-8 following Visit 1, Visit 2, and Visit 1 and Visit 2 combined.
2. EOM 5.2: Average number of consecutive days of fever (temperature $\geq 38.0^{\circ}\text{C}$ or $\geq 100.4^{\circ}\text{F}$) per subject for fever starting on 3-8 days following Visit 1, Visit 2, and Visit 1 and Visit 2 combined. *Note: fever starting on day 3-8 could continue through day 8.*
3. EOM 5.3 Proportion of children with medical care utilization (telephone call, medical office visit, emergency department visit, or hospital admission) for fever on 3-8 days following Visit 1, Visit 2, and Visit 1 and Visit 2 combined).

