4.2 Sample Size and Power

Allowing for a 10% drop out rate given an initial N=280, there should be approximately 252 children enrolled into the study. If the true proportion of children who have fever on day 1 and/or day 2 after the first and/or second visit in the simultaneous group is 36% and the true proportion in the sequential group is 18%, then there is 90% power to reject the null hypothesis of no difference with N=126 per group with a two-sided alpha 0.05 level. This is based upon using a Mantel-Haenszel statistic in a stratified analysis to control for sites.

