8.3 Exploratory Objectives

There are eight exploratory objectives for this study.

- a) The first exploratory objective (EO 1) is to compare the height and duration of fever on day 1 and/or day 2 after Visit 1 and Visit 2 (separately and combined) in the simultaneous versus sequential group. The average peak temperature of each child with fever during the risk window of days 1 and 2 (temperature $\geq 38.0^{\circ}\text{C}$ or $\geq 100.4^{\circ}\text{F}$) and the total number of fever degree-days (temperature $\geq 38.0^{\circ}\text{C}$ or $\geq 100.4^{\circ}\text{F}$) following Visit 1, Visit 2 and Visit 1 and 2 combined will be presented by simultaneous and sequential vaccination groups. These six comparisons will be made using a Mann-Whitney U/Wilcoxon rank-sum test.
- b) The second exploratory objective (EO 2) is to compare the use of antipyretics for fever on day 1 and/or day 2 after Visit 1 and Visit 2 (separately and combined) in the simultaneous versus sequential group. The use of antipyretics for fever on day 1 and/or day 2 after Visit 1 and Visit 2 (separately and combined) will be presented for the simultaneous versus sequential group in tables. These three proportions of children with antipyretic use on day 1 and/or day 2 following Visit 1, Visit 2, and Visit 1 and Visit 2 combined will be compared using a Mantel-Haenszal statistic in a stratified analysis by site between the simultaneous and sequential vaccination groups.
- c) The third exploratory objective (EO 3) is to describe and compare the level of severity of fever following Visit 1 and Visit 2 separately, in the simultaneous versus sequential group. Fever will also be assessed at different levels of severity (Grades 1, 2, and 3) on day 1 and/or day 2 and days 3-8 following Visit 1 and separately for Visit 2. The grade levels are defined in Table 2.

Temporal Artery Temperature	None	Mild (Grade 1)	Moderate (Grade 2)	Severe (Grade 3)
°C	≤ 37.9	$\geq 38.0 - \leq 38.5$	$\geq 38.6 - \leq 39.5$	≥ 39.6
°F	≤ 100.3	$\geq 100.4 - \leq 101.3$	$\geq 101.4 - \leq 103.1$	≥ 103.2

There will be six (day 1 and/or day 2, days 3-8, and days 1-8 following Visit 1 and separately for Visit 2) statistical comparisons performed at the alpha 0.05 level. These group comparisons will be made using a Mantel-Haenszel statistic (row mean scores difference with standardized midranks scores [modified ridit scores]) in a stratified analysis by site to control for the randomization blocks.

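### The peak-temperature test (EOM 1.1) is confined to children who became febrile, so it is not a randomized comparison and rests on about 68 of 252 children; an all-children comparison can be added from readings already collected

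*Combined protocol and SAP*

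**What the plan says.** SAP 3.3 defines the endpoint as "EOM 1.1: Average peak temperature of children with fever", with fever meaning at least 38.0 °C on day 1 and/or day 2. The outcome list in protocol 2.1 carries the same restriction. SAP 8.3 a) repeats it ("The average peak temperature of each child with fever during the risk window of days 1 and 2") and compares the arms by a rank-sum test after Visit 1, after Visit 2 and for both visits combined. The other three of the six rank-sum tests for EO 1 concern fever degree-days (EOM 1.2).

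The analysis sentence in protocol 6.2.5 is looser. It reads "For exploratory objective 1 the average peak temperature on day 1 and/or 2 following Visit 1, Visit 2 and Visit 1 and 2 combined" and does not mention the restriction to febrile children.

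Protocol 5.4 says that parents "will measure and record the participant's temperature at approximately the same time each day", from Day 1 to Day 8 after both visits. It expressly includes children in the simultaneous arm, who receive no vaccine at Visit 2. A day 1-2 peak is therefore planned for every child, febrile or not.

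**The concern.** Two features of the febrile-only test are a problem. First, being febrile on day 1 or 2 is the primary outcome and arises after randomization. If the schedules differ in how many children they make febrile, the two febrile subsets need not be comparable. If the simultaneous schedule carries some children just past 38.0 °C, their low fevers enter that arm's febrile group and pull its typical height down, which can hide a real upward shift.

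Second, the test is small. Most children's readings are left out, and the Visit 2 comparison would rest on a handful of children. A non-significant result could be read as showing no difference in the height of fever, when the test had little chance of showing one. This matters because protocol 1.2 treats fever as a possible proxy for febrile seizure risk. The stakes are still limited: EO 1 is exploratory, has no stated power, and does not touch the primary or secondary analyses.

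**Working it through.** **Inputs from the documents (SAP 4.2).** The plan states "there is 90% power to reject the null hypothesis of no difference with N=126 per group with a two-sided alpha 0.05 level", with 36% febrile in the simultaneous arm and 18% in the sequential arm, and a 10% dropout from 280.

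**Reproducing the plan's figure.** 280 × 0.90 = 252, or 126 per arm. The standard two-proportion formula without continuity correction, at 0.36 v 0.18 with 126 per arm and two-sided 0.05, gives power 0.9006. The stated 90% is reproduced.

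**Children entering EOM 1.1 (both visits combined).**
- Simultaneous: 126 × 0.36 = 45.4.
- Sequential: 126 × 0.18 = 22.7.
- Total about 68 of 252, so about 184 children's peaks are unused.

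**Assumptions.** The SD and shape of peak temperature are not in the documents. The power figures below are simulations of a two-sided rank-sum test at 0.05 with 126 per arm, temperatures rounded to 0.1 °C, and the share at or above 38.0 °C set to 36% v 18%.

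| Assumed model | Febrile-only peak | All-children peak |
|---|---|---|
| Normal location shift, SD 0.4 to 0.8 °C | 16-17% | about 99% |
| Mixture; febrile mean excess over 38.0 °C of 0.9 v 0.6 °C | about 25% | about 75% |
| Mixture; febrile heights equal, only the febrile share differs | about 5% | about 70% |

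The mixture models draw afebrile peaks from a normal distribution (mean 37.0, SD 0.4 °C) cut off below 38.0 °C, and febrile peaks as 38.0 °C plus an exponential excess.

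**Why the shift model gives so little.** The shift matching 36% v 18% is z(0.82) − z(0.64) = 0.915 − 0.358 = 0.557 SD. Above a cut a exceeded by a share p, the mean excess of a normal variable is φ(a)/p − a in SD units. For p = 0.36 and a = 0.358 this is 0.68. For p = 0.18 and a = 0.915 it is 0.54. The febrile subsets differ by only 0.14 SD, although the arms differ by 0.557 SD.

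**How to read the third row.** There, fever height is the same in both arms by construction. The 5% is the test's type I error, not lost power, and the 70% comes entirely from the difference in fever incidence.

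**Visit 2 alone.** Assume 7.5% febrile in the sequential arm (the figure for influenza vaccine alone in protocol 1.1) and a background of 2-5% in the simultaneous arm (an assumption; the documents give none).
- Expected febrile children: 126 × 0.075 = 9.45, against 126 × 0.02 = 2.5 to 126 × 0.05 = 6.3.
- Febrile-only test: significant in about 2-4% of runs.
- All-children test, normal shift: about 37% (5% background) to 99.8% (2%).
- All-children test, equal-height mixture: about 6% to 12%.

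**What the plan already has beyond fever yes/no.** EOM 1.2 is defined per subject. If afebrile children score 0, a zero-floored height score used as a proxy for it has about 89-93% power at 36% v 18%. The SAP does not state that scoring rule. EO 3 compares ordered grades, including a category for no fever. Both use height above 38.0 °C and neither uses readings below it.

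**The case against.** EO 1 asks about the height of fever, and only a febrile child has a fever height. On that view EOM 1.1 matches its objective, and an all-children peak answers a different question, partly repeating the primary test. This stands, and it is why the all-children comparison should be added with its meaning stated and the febrile-only summary kept. It does not rescue the febrile-only significance test, which remains a comparison of subsets chosen by a post-randomization outcome.

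Readings below 38.0 °C are also less complete as peaks. Extra readings are taken only when a child feels warm, a repeat is required only at 38.0 °C and above or 35 °C and below, and the trial is open-label, so a maximum could shift through unequal checking. This is a fair caution for interpretation; the same checking also affects febrile peaks.

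A reader might infer more than the documents support:
- That EOM 1.1 is the plan's only quantitative comparison of temperature. It is not: degree-days are tested in the same set of six, and EO 3 compares grades.
- That the gap between 5% and 70% is power thrown away. With equal fever heights, 5% is the correct rejection rate for a question about height.
- That protocol 6.2.5 shows an unrestricted analysis was intended. The protocol's own EOM 1.1 has the restriction, so that sentence may be shorthand. The wording needs aligning, but it is not evidence of intent.
- That the all-children test reliably rescues Visit 2. Its power there runs from about 6% to over 99% depending on the model.

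**Conclusion.** The point holds in a limited form. EOM 1.1 as tested compares subsets defined by the primary outcome after randomization, with about 45 v 23 children at the plan's own rates. Where the arms truly differ in temperature, its power is about 16-17% (normal shift) or about 25% (0.9 v 0.6 °C mean excess), against about 99% and 75% for all children. These figures depend on assumed distributions and are illustrations, not bounds. The larger numbers partly restate fever incidence. No planned analysis uses the recorded readings below 38.0 °C. This is a cheap improvement to an exploratory objective, not a flaw in the trial's main inference.

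**What to change.** In SAP 8.3 a), add a between-arm comparison of each child's highest recorded day 1-2 temperature after Visit 1, after Visit 2 and combined, in all children with a recorded reading, and report the difference with its 95% CI. Keep the febrile-only peak as a descriptive summary by arm, labelled as conditional on fever and not a randomized comparison. State in EOM 1.2 that afebrile children score 0, so that it includes all randomized children with readings. Bring protocol 6.2.5 into line with this wording. Leave the primary endpoint as it is.

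The cost is text only, since the readings are already planned in both arms. The downsides are a few more exploratory tests, and a peak measure that mixes how many children are febrile with how high their temperatures go; the SAP should say so where the result is reported.

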4.3 Randomization

Participants will be randomized (1:1) to receive either PCV13, DTaP and IIV simultaneously or sequentially (PCV13 and DTaP followed by IIV ~2 weeks later) using a permuted block randomization scheme stratified by study site (i.e., Duke University Medical Center and Kaiser Permanente Northern California). The first 10 children enrolled in the pilot at Duke University will be randomized in a block of 10 such that 5 children will receive simultaneous vaccination and 5 will receive sequential vaccination. The project statistician at Duke University will generate permuted block randomization schemes, which will be uploaded to REDCap. The randomization schedule will not be available to the study staff, so the next randomization

allocation will not be known before randomization occurs. Following confirmation of study eligibility criteria during Visit 1, participant randomization will be through REDCap with treatment allocation recorded on the CRF. This study will be open label and study staff and subjects will not be blinded to treatment arm assignments.

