5.2 Analytic Issues

There are two sites participating in the study and analysis of the primary objective will be stratified by site to account for this unit of randomization. Secondary data objectives may be stratified by site when applicable. There is one primary objective evaluated at the alpha 0.05 level and no adjustments to the alpha level will be made for secondary and exploratory analyses.

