office visit, emergency department visit or hospital admission) on day 1 and/or day 2 following Visit 1, Visit 2 and Visit 1 and 2 combined. Medical utilization for fever will be counted as positive for this analysis if onset of fever on day 1 and/or day 2 plus medical utilization on day 1, day 2 or day 3 after fever. Medical care related to fever will be determined by report on the diary.

Proportions will be compared between the simultaneous and the sequential vaccination groups using a Mantel-Haenszal statistic (three tests) in a stratified analysis by site to control for the randomization blocks. The duration of fever will be compared between groups using a Mann-Whitney U/Wilcoxon rank-sum test (three tests).

No adjustments will be made to the alpha level (two-sided alpha=0.05) for these secondary objectives.

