There will be three statistical comparisons performed (mean duration of any fever starting on days 3-8 following Visit 1, Visit 2, and Visit 1 and Visit 2 combined) at the alpha 0.05 level. These group comparisons will be made using a Mann-Whitney U/Wilcoxon rank-sum test.

3. Medical care utilization for fever: The proportion of children with medical care utilization determined by report on the diary (telephone call, medical office visit, emergency department visit, or hospital admission) for fever on at least one

day during days 3-8 following Visit 1, Visit 2, and Visit 1 and Visit 2 combined, will be presented in tables or the simultaneous versus sequential group. There will be three statistical comparisons performed. These group comparisons will be made using a Mantel-Haenszal statistic in a stratified analysis by site to control for the randomization blocks.

- f) The sixth exploratory objective (EO 6) is to describe and compare the occurrence of solicited systemic adverse events (excluding fever) on days 1-8 after Visit 1 and Visit 2 in the simultaneous versus sequential group. Table 3 below lists the solicited adverse events to be collected.

Table 3: Solicited Systemic Adverse Events				
	None	Mild (Grade 1)	Moderate (Grade 2)	Severe (Grade 3)
Fussiness or Irritability	None	Less playful than usual but not requiring more attention and able to console	Requiring increased attention but able to console	Unable to console
Change in eating habits	None	Eating less than normal for 1 to 2 feeds/meals	Missed 1 or 2 feeds/meals completely	Refuses ≥ 3 feeds/meals or refuses most feeds/meal
Drowsiness or Sleepiness	None	Drowsiness but still interested in surroundings and did not miss feed or meal	Not interested in surroundings or did not wake up for a feed or meal	Sleeps most of the time or difficult to wake up

Listings of all solicited adverse events will be produced showing vaccination group, date of onset, date of resolution, and highest grade level. The frequency and percentage of the highest grade level for participants will be presented by each of the three solicited adverse events. There will be three statistical comparisons made using a Mantel-Haenszal statistic (row mean scores difference with standardized midranks scores [modified ridit scores]) in a stratified analysis by site to control for the randomization blocks.

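### The rank-sum tests for fever duration, peak temperature and degree-days pool the two sites although randomisation is stratified by site; the main cost is power, and the priority is minor

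*Combined protocol and SAP*

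**What the plan says.** SAP 4.3 allocates children 1:1 "using a permuted block randomization scheme stratified by study site"; protocol 5.5.1 agrees. The SAP then stratifies by site for the primary comparison (8.1), SO 1 and the SO 2 proportions (8.2), and EO 2, EO 3, EO 4, the EO 5 proportions, EO 6 and EO 8 (8.3). In most of these places it gives control for the randomisation blocks as the reason.

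Twelve rank comparisons have no site term:
- SAP 8.2 b), day 1-2 duration (SOM 2.2, secondary): "The duration of fever will be compared between groups using a Mann-Whitney U/Wilcoxon rank-sum test (three tests".
- SAP 8.3 a), peak temperature and degree-days (EOM 1.1 and 1.2): "These six comparisons will be made using a Mann-Whitney U/Wilcoxon rank-sum test".
- SAP 8.3 e), day 3-8 duration (EOM 5.2), three tests: "These group comparisons will be made using a Mann-Whitney U/Wilcoxon rank-sum test".

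Protocol 6.2.4 and 6.2.5 name the same test, so this is not a transcription slip. The only other unstratified comparison in SAP 8 is Fisher's exact test for EO 7, and there the SAP gives its reason (few expected events).

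SAP 5.2 does not settle the matter: "Secondary data objectives may be stratified by site when applicable". That is permissive, and it does not mention exploratory objectives. For ordered grades, by contrast, SAP 8.3 c) uses a "Mantel-Haenszel statistic (row mean scores difference with standardized midranks scores [modified ridit scores]) in a stratified analysis by site".

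**The concern.** An analysis should normally reflect the factor used to stratify the randomisation. Two things can follow when a rank test pools the sites.

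First, if temperatures or durations differ by site, that difference adds noise to the pooled ranks and the test loses power. Few children are available to absorb the loss: 36% and 18% of 126 per arm is about 45 and 23 febrile children for the combined window.

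Second, peak temperature and both durations are compared only among children with fever, a subset formed after randomisation. Stratified 1:1 allocation balances the sites among all randomised children, not among the febrile ones. If the febrile children's site mix differs between arms, a site difference can leak into the arm comparison. All twelve tests run at an unadjusted two-sided 0.05.

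**Working it through.** **The plan's own figure.** The documents state power only for the primary comparison. With p1 = 0.36, p2 = 0.18, n = 126 per arm and mean proportion 0.27:

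power = Φ{[0.18 − 1.96·√(2·0.27·0.73/126)] / √[(0.36·0.64 + 0.18·0.82)/126]} = Φ{(0.18 − 0.1096)/0.0548} = Φ(1.285) = 90.06%.

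The stated 90% reproduces. It concerns the site-stratified primary test and is not touched by this point.

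**Inputs for the rank tests.** From the documents: site sizes 160 and 120 (protocol 4.3), 1:1 allocation, fever 36% v 18%, 10% dropout (SAP 4.2). Assumed: peak temperature in febrile children is 38.0 °C plus an exponential excess with mean and SD 0.5 °C, rounded to 0.1 °C, with site shifts of 0 to 0.5 °C.

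**Statistics.** The pooled test is the usual tie-corrected rank sum. The stratified (van Elteren) test uses Z = Σ w_s(W_s − E_s)/√(Σ w_s²V_s), with w_s = 1/(N_s + 1), where W_s is the rank sum within site s, and E_s and V_s are its null mean and tie-corrected variance.

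**Power.** Same fever rates at both sites, arm effect 0.25 °C, 160/120 children:

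| Site shift (°C) | Pooled | Stratified |
|---|---|---|
| 0 | 79% | 78% |
| 0.1 | 77% | 78% |
| 0.2 | 75% | 79% |
| 0.3 | 69% | 78% |
| 0.5 | 56% | 78% |

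Simulation error is about 0.6 points (√(0.78·0.22/5000)). After 10% dropout (144/108), the 0.5 °C row becomes 52% v 74%. A separate run with a gamma excess and an arm effect of 0.35 °C gave 70% v 84% at 0.5 °C.

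**Type I error.** What matters is the smaller site's share of the febrile children in each arm.
- Same fever pattern at both sites: 120/280 = 43% in both arms. Pooled error stays at about 4-5%.
- Moderate pattern (simultaneous v sequential: 45% v 18% at the larger site, 24% v 18% at the smaller; 72 and 54 children per arm). Simultaneous share: 54·0.24/(72·0.45 + 54·0.24) = 12.96/45.36 = 29%. Sequential share: 9.72/22.68 = 43%. Pooled error is 5.8% at a 0.2 °C shift and 6.8% at 0.3 °C.
- Extreme pattern (45% v 13% and 24% v 24%; 80 and 60 per arm). Shares: 14.4/50.4 = 29% and 14.4/24.8 = 58%. Pooled error is about 11-14% at 0.2-0.3 °C (repeat runs span 10-15%), against about 5% stratified.
- All randomised children ranked, with the afebrile at zero: pooled error 3.5-5.4%, so no inflation.

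**Duration.** In whole days with heavy ties (a geometric distribution, assumed), the two tests differ by about 1 point of power. Pooled error is 6.5% even under the extreme pattern.

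**Sparse Visit 2 comparisons.** Take 7.5% fever in the sequential arm (protocol 1.1, influenza vaccine alone in the earlier observational study) and assume 4% in the arm with no vaccine at that visit. With 72 and 54 per arm, the chance that some site has an empty arm is 1 − (1 − 0.96^72)(1 − 0.96^54)(1 − 0.925^72)(1 − 0.925^54) = 1 − 0.947·0.890·0.996·0.985 ≈ 17%. Such a site contributes nothing to the stratified test. With no site shift, pooled v stratified power is 47% v 42% at an arm effect of 0.5 °C and 81% v 75% at 1.0 °C.

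**The case against.** The best defence is that little is likely to be lost. The protocol supplies one thermometer model to every family (5.4) and buys DTaP and influenza vaccine for the study so that both sites use the same products. Both steps should narrow site differences, and no site-specific temperature data suggest a large one. At shifts of 0.1-0.2 °C the power gap is 0-4 points. A shift of 0.5 °C equals a full SD of the assumed excess. Nine of the twelve tests are exploratory, and the durations are so heavily tied that stratifying hardly changes them. Stratifying also has a price where fever is rare. All of this stands, and it keeps the priority low.

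A reader might infer that pooling generally turns a site difference into an apparent arm difference. The documents do not support that. It takes a febrile-only comparison, a site difference in the outcome and a febrile site mix that differs between arms, whether by chance or because the schedule's effect on fever differs by site. Nothing in the documents points to a threefold effect at one site and none at the other. For degree-days the outcome is defined per subject (SAP 3.3); if afebrile children count as zero, no inflation is expected.

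The defence does not explain why the rank tests alone drop site without comment when the SAP already holds a stratified alternative.

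**Conclusion.** The inconsistency is real and covers twelve tests, three of them on a secondary outcome. Its main effect is lost power for peak temperature: about 4 points at a 0.2 °C site shift, about 10 at 0.3 °C and about 22 at 0.5 °C. Type I error is a conditional and usually small problem: about 6% in a moderate case, and 11-14% only under an extreme arm-by-site fever pattern. These sizes rest on assumed site shifts and an assumed distribution. They were worked out for peak temperature and should not be carried over to duration, where the difference is about 1 point of power.

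Two further inferences do not hold. Stratification is not free everywhere, as the Visit 2 figures show. And the primary result is not in doubt, because its comparison is already stratified by site. Priority: minor.

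**What to change.** In SAP 8.2 b) and 8.3 a) and e), replace the rank-sum test with the site-stratified van Elteren test, that is, row mean scores with modified ridit scores stratified by site, as specified for EO 3, EO 6 and EO 8. Reword SAP 5.2 so that between-group rank comparisons for secondary and exploratory objectives will be stratified by site. Making only its present sentence mandatory would reach SOM 2.2 but not EOM 1.1, 1.2 or 5.2. State also whether afebrile children enter degree-days as zero.

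The cost is a few lines of SAP text and no new data or method, though the documents do not say whether any code exists yet. In sparse Visit 2 comparisons the stratified test gives up about 5-7 points of power when the sites do not differ; there the unstratified test can be reported alongside it.
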